2.5 Schedule of Visits and Assessments

3. Study Treatments

In this multiple arm multiple dose escalation study QR-110 will be administered by unilateral IVT injection. Each subject will receive up to 4 doses of QR-110 in their worse eye (defined in Section 8.1 of the SAP) at least 3 months apart and will be assessed for safety and tolerability at follow-up visits. Up to 3 dose levels will be tested (loading dose/maintenance dose):

- Low Dose: One 160 µg loading dose, followed by up to three 80 µg maintenance doses
- Mid Dose: One 320 µg loading dose, followed by up to three 160 µg maintenance doses
- High Dose: One 500 µg loading dose, followed by up to three 270 µg maintenance doses

QR-110 Solution for IVT Injection, 10 mg/mL and diluent, will hereby be referred to as IVT injection.

As noted previously in Section 2.3, no subjects were treated at the high dose, therefore only the low dose and mid dose will be considered within the statistical TLFs for this study.

4. Sample Size and Power Considerations

This is a phase 1b/2 safety study designed to evaluate the safety, tolerability and PK of QR-110. The sample size is not based on power calculations. It is chosen based on clinical experience and considered to be adequate to fulfill the objectives of the study.

Twelve subjects are planned to be enrolled in the study. However, depending upon observed results, the DMC and Sponsor Medical Monitor may add subjects as indicated in Section 4.2.2.2 of the protocol, for a maximum number of subjects up to a total of n = 18.

4.1 Randomization and Masking

No randomization or masking is used for this phase 1b/2 open label safety study.

Evaluators responsible for grading mobility course videos and reviewing and interpreting ophthalmologic imaging (FST, SD-OCT, PLR, OCI, ERG, NIRAF) will be masked to which eye is the treated eye for the entire course of the study to ensure that grading videos and ophthalmologic assessments are unbiased.

4.2 Replacement of Subjects

Subjects who discontinue from the study without receiving any study drug will be replaced. Subjects discontinuing the study before the full course of study drug may be replaced by a subject who will be assigned the same dose as the subject being replaced. The decision for replacement will be made by the Sponsor based on available data and perceived need for additional data.

5. Data Preparation

All reported study data will be recorded on the electronic case report forms (eCRFs)

Only the

Principal Investigator and authorized study staff according to the Delegation of Responsibilities log are entitled to make entries in the eCRF.

After data are entered into the clinical study database, electronic edit checks and data review will be performed. All data validation specifications and procedures are detailed in the Data Validation Manual as a separate document. When the database has been declared to be complete and accurate, the database will be locked. Any changes to the database after data have been locked can only be made with the approval of the Sponsor in consultation with SDC.

All analyses outlined in this document will be carried out after the following have occurred:

- All data management requirements are met according to SDC standard operating procedures, including data entry, performance of edit and validation checks, documentation and resolution of data queries, and database lock with written authorization provided by appropriate SDC and Sponsor personnel;
- Protocol deviations have been identified and status defined (major/minor deviations);
- Analysis populations have been determined.

6. Analysis Populations

The analysis population definitions in the SAP will supersede the analysis definitions in the protocol.

6.1 All Enrolled Subjects Population

The All Enrolled Subjects population will consist of all subjects who have provided informed consent, including screen failures as well as subjects who received any QR-110 IVT injection.

6.2 Safety Population

The population for safety analysis will consist of all subjects who received any QR-110 IVT injection.

6.3 Efficacy Evaluable Population

The population for efficacy (clinical activity) analysis will consist of all subjects who received any QR-110 with at least one baseline and one post-baseline efficacy observation or measurement.

6.4 Pharmacokinetic (PK) Population

The population for PK analyses will consist of all subjects who received QR-110 and who have measurable drug concentrations (ie, above the lower limit of quantification) in blood samples.

7. General Statistical Considerations

7.1 Study/Treatment Eye Definition and Unit of Analysis

The study eye will be the treated eye for all efficacy and safety summaries. The study eye will always be referred to as the treated eye on TLFs and is defined as the eye with the worse visual acuity at

Screening. If both eyes have the same visual acuity, the Investigator should determine the eye with the worse visual function, according to other measures of ophthalmic function (FST or mobility course score). If the visual function is the same per the Investigator's assessment, then the treated eye will be determined at Investigator discretion.

The unit of analysis for all ocular endpoints will be the eye level. All ocular endpoints will be summarized by eye and by dose group and cohort (ie, adult versus pediatric) for the treated eye and contralateral eye where appropriate. Subject level information, non-ocular AEs, medical history,-

7.2 Missing or Inconclusive Data Handling

Other than the imputations described within Section 7.2.1, no special handling of missing data will be made and analyses will be conducted using observed values only.

7.2.1 MISSING MOBILITY COURSE COMPOSITE SCORE IMPUTATIONS FOR CENTRAL READING CENTER GRADING

7.3 Definition of Baseline

Baseline is defined as the last measurement prior to the first dose of study drug in the treated eye for IOP, laboratory parameters, and the safety endpoints slit lamp biomicroscopy, posterior segment/fundus exam, vital signs, and ECG . For ophthalmic parameters BCVA, FST, mobility course, OCI and PLR measured at Screening and Visit 2 (Day 1) the average will be defined as baseline. For other ophthalmic parameters, NIRAF, SD-OCT, and ERG, planned to be done once at baseline, the average will be defined as baseline if the exam is repeated. Change from baseline will be calculated as follow-up visit/time point minus baseline visit/time point.

7.4 Data Analysis Conventions

All data analysis, data summaries, and formal listing preparation will be performed by Statistics & Data Corporation (SDC) for DMC meetings, Interim Analyses and upon the completion of the study. Analyses after the study is completed will be done with a locked database. Statistical programming and analyses will be performed using SAS® version 9.4 or higher. Output will be provided in Rich Text Format (RTF) for tables and Portable Document Format (PDF) for tables, listings, and figures using landscape orientation. All study data will be listed by subject, sorted by cohort/dose level (in the order of adult cohort 1 [low dose, 160 µg loading dose, followed by up to three 80 µg maintenance doses], pediatric cohort 1 [low dose], adult cohort 2 [middle dose, 320 µg loading dose, followed by up to three 160 µg maintenance doses], and pediatrics cohort 2 [middle dose]), and by eye (OD, OS and OU where applicable) and visit unless otherwise specified. Listings may also include time point, age, and sex where appropriate.

Summaries for continuous and ordinal variables will include the number of observations (n), arithmetic mean, standard deviation (SD), median, minimum, and maximum. Minima and maxima will be reported with the same precision as the raw values; means and medians will be presented to one additional decimal place than reported in the raw values. Standard deviations will be presented to two additional decimal places than reported in the raw values. Imaging data will be rounded to 3 decimal places then follow the previously mentioned conventions. Summaries for discrete variables will include frequency counts and percentages. All percentages will be rounded to one decimal place (i.e., XX.X%). Change from baseline will be calculated as follow-up minus baseline.

All continuous efficacy endpoints will be summarized using the following descriptive statistics: number of subjects (N), mean, standard deviation, standard error, median, minimum, maximum and 95% confidence intervals (CI) for the mean. Categorical endpoints will be summarized using: number of subjects, frequency, percentages and 95% asymptotic confidence intervals. If data appear highly skewed, natural log or other transformation may be used to compute summary statistics.

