## 10.8 Efficacy Analyses

The efficacy evaluations will include:

- Secondary efficacy evaluations
  - BCVA
  - FST
  - PLR
- Exploratory efficacy evaluations

Descriptive statistics of clinical efficacy will be tabulated by dose group, and if appropriate, for dose groups combined.

All continuous endpoints will be summarized using the following descriptive statistics: number of subjects, mean, standard deviation, standard error, median, minimum, maximum and 95% confidence intervals for the mean. Categorical endpoints will be summarized using: number of subjects, frequency, percentages and 95% confidence intervals. If data appear highly skewed, natural log or other transformation may be used to compute summary statistics.

Continuous efficacy endpoints will be summarized and may be analyzed using appropriate parametric or nonparametric inference tests.

Details of the statistical analyses can be reviewed in the SAP.

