2.3 Study Cohorts and DMC Review Schedules

QR-110 will be administered at up to 3 escalating dose levels and the study will include up to 6 cohorts (up to 3 adult cohorts and up to 3 pediatric cohorts). Each cohort will have at least 2 subjects and each dose level will be tested in 1 adult cohort and 1 pediatric cohort (Table 1). Dose escalation will proceed as described in Section 4.2.1.5 of the protocol. QR-110 will be administered via unilateral IVT injection

in the subject's worse eye (defined in Section 8.1 of the SAP) every 3 months and each subject will receive up to 4 doses of study drug.

While the protocol allows testing of up to 3 dose levels, no dose escalation to the highest dose was performed based on interim study results.

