7.6 Interim Analyses

An interim analysis of all outputs was conducted after the eighth subject in the study had at least 3 months of data in accordance with SAP version 1.0. The interim analysis included all available study data (all monitored and cleaned) at the time of the data snapshot, .

An additional interim analysis (interim analysis 2) of all outputs was performed using all available data (all monitored and cleaned) from all 11 subjects at the time of the data snapshot (ie, after mid-August 2018). SAP Version 1.0 was in effect at the time of this interim analysis.

A third interim analysis, consisting of all outputs produced for interim analysis #2, will be performed once the last subject has completed Visit 15 (end of study visit) and there is a soft lock. This third interim analysis (planned for August 2019) will consist of all outputs for interim analysis 2 and will include all available study data (all monitored and cleaned) at the time of the data snapshot.

No alpha or family-wise error rate adjustments are made for interim analyses at the data for this early phase 1b/2 trial as all analyses are exploratory.

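### SAP 7.4 sets asymptotic 95% confidence intervals for proportions in groups of 2 to 11 subjects, where they have zero width, leave the 0–100% range, or cover well below 95%

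*SAP*

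**What the plan says.** SAP 7.4 (Data Analysis Conventions) gives the rule in the paragraph on efficacy endpoints: "Categorical endpoints will be summarized using: number of subjects, frequency, percentages and 95% asymptotic confidence intervals". Protocol 10.8 has the same sentence without the method: "Categorical endpoints will be summarized using: number of subjects, frequency, percentages and 95% confidence intervals". SAP section 1 says that its methods take precedence over the protocol's, so the asymptotic form governs. No exact, score or other small-sample alternative appears in the available text.

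The group sizes follow from four statements in the SAP:

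- Section 2.3: "Each cohort will have at least 2 subjects and each dose level will be tested in 1 adult cohort and 1 pediatric cohort".
- Section 3: nobody received the high dose, so the outputs cover only the low and middle doses.
- Section 7.6: the second interim analysis took data "from all 11 subjects at the time of the data snapshot".
- Section 7.4: summaries are shown by cohort and dose level, for adults and pediatric subjects separately and combined.

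**The concern.** An asymptotic interval relies on a large sample, and no row of these tables has one. The Wald interval takes its width from the observed proportion, so the width is zero whenever that proportion is 0 or 1. In a group of two to five subjects this will happen often. Near the extremes the symmetric form also runs past 0% or 100%.

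This SAP plans no inferential tests, so these intervals are its only stated measure of uncertainty for a categorical efficacy result. If they are too narrow, a reader comparing dose groups or age groups sees more certainty than the data hold, under a 95% label that is not true.

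**Working it through.** **Inputs.** Total n = 11 (SAP 7.6). Two dose levels (SAP section 3), one adult and one pediatric cohort each, at least 2 subjects per cohort (SAP 2.3). Single-cohort sizes are not stated, but they are bounded. With four cohorts of at least 2, the largest is 11 − 3×2 = 5. A pair of cohorts (a dose group or an age group) holds between 2×2 = 4 and 11 − 4 = 7. The 95% level is taken as two-sided, z = 1.96. The true proportion p is not given, so a range is shown.

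**Assumption.** The SAP names no formula. Asymptotic is read as the Wald interval, with p̂ = x/n:

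p̂ ± 1.96 × √[p̂(1 − p̂)/n]

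The exact (Clopper-Pearson) limits are the 2.5% point of Beta(x, n − x + 1) and the 97.5% point of Beta(x + 1, n − x). For x = 0 the upper limit is 1 − 0.025^(1/n).

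**Individual intervals.** Two worked cases:

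- 4/5: 0.8 ± 1.96 × √(0.8 × 0.2/5) = 0.8 ± 0.351, which is 44.9% to 115.1%.
- 0/5: Wald gives 0 ± 0. The exact upper limit is 1 − 0.025^(1/5) = 52.2%.

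| Result | Wald | Exact |
|---|---|---|
| 0/2 | 0% to 0% | 0% to 84.2% |
| 1/2 | −19.3% to 119.3% | 1.3% to 98.7% |
| 0/5 | 0% to 0% | 0% to 52.2% |
| 1/5 | −15.1% to 55.1% | 0.5% to 71.6% |
| 4/5 | 44.9% to 115.1% | 28% to 99.5% |
| 0/11 | 0% to 0% | 0% to 28.5% |
| 1/11 | −7.9% to 26.1% | 0.2% to 41.3% |

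**Chance of a zero-width interval.** This is (1 − p)^n + p^n. At p = 0.2 it is 0.64 + 0.04 = 68% for n=2, 0.3277 + 0.0003 = 33% for n=5, 26% for n=6 and 9% for n=11.

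**Actual coverage.** Sum the binomial probabilities of every x whose interval contains p. For n=5 and p=0.2, only x = 1, 2 and 3 qualify: 0.4096 + 0.2048 + 0.0512 = 66.6%. For n=2, only x = 1 can qualify, so coverage is at most 2p(1 − p), which peaks at 50%.

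| n | p=0.1 | p=0.2 | p=0.3 | p=0.5 | Mean over p |
|---|---|---|---|---|---|
| 2 | 18% | 32% | – | 50% | 33% |
| 3 | 24% | 48% | 63% | 75% | 50% |
| 4 | 34% | 56% | 68% | 88% | 58% |
| 5 | 40% | 67% | 80% | 94% | 64% |
| 6 | 47% | 72% | 87% | 78% | 68% |
| 11 | 68% | 90% | 87% | 94% | 78% |

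The mean runs over p from 0.001 to 0.999. The dash marks a value not tabulated. The stated 95% is not reached on average at any of these sizes.

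**Alternatives on the same enumeration (n from 2 to 11).**

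- Clopper-Pearson: lowest coverage over p is 97.5% for n=2 to 5, 96.6% for n=6 and 95.8% for n=11. No interval has zero width and none leaves 0–100%.
- Wilson score: mean coverage is about 95.5%, lowest coverage 82% to 84%, and limits stay within 0–100%.
- Wald with a continuity correction of 0.5/n: mean coverage is only 72% (n=2), 82% (n=5) and 88% (n=11).

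**The case against.** The case for leaving the text alone, or treating it as a small clarification, has several parts.

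- **Few outputs are affected.** The sentence sits in the efficacy paragraph. Adverse event summaries, including the primary endpoint, are planned as counts and percentages without intervals. Most secondary efficacy endpoints are continuous changes from baseline. The visible categorical efficacy outputs are mainly the BRVT (rudimentary vision test) category frequencies and the vision-category shifts in SAP 14.1, which do not themselves ask for intervals. This stands, and it limits the reach of the problem. The revision history also lists a responder analysis, but its text is not in the available copy and may state its own method.
- **Nothing depends on the intervals.** The trial is not powered for efficacy, this SAP plans no tests, and escalation rests on safety review. This also stands. Even so, an interval labelled 95% makes a claim about coverage whether or not a test follows.
- **The reader sees the counts.** A 0% to 0% interval beside 0/5 looks plainly degenerate. That is fair for the extremes, but less so for 1/11 or 2/11, where the interval looks plausible and is still too narrow.
- **The formula is not named.** A Wilson interval is also derived asymptotically and would avoid zero width and impossible limits. That is possible, but Wald is the usual meaning when asymptotic is set against exact. If Wilson was meant, the SAP needs to say so.
- **Coverage is not low everywhere.** At p=0.5 it is 94% for n=5 and n=11. This is correct. From n=5 upward the shortfall concerns low and high proportions and the average. At n=2 and n=3 coverage never exceeds 75%.

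**Conclusion.** The concern holds. The SAP chose a large-sample interval that the protocol did not ask for, in a trial where no summary group exceeds the 11 subjects counted at the second interim analysis. Followed as written under the Wald reading, the rule gives a zero-width interval whenever x = 0 or x = n, and limits outside 0–100% for results such as 1/2, 4/5 and 1/11. Mean coverage runs from 33% at n=2 to 78% at n=11.

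The conclusion rests on two assumptions: that asymptotic means Wald, and that the cohort sizes lie within the 2 to 5 implied by 11 subjects in four cohorts of at least 2. The continuity-corrected form would not rescue the rule; a Wilson interval largely would. The error affects the descriptive precision of categorical efficacy summaries. It does not affect the primary safety result or any decision rule.

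**What to change.** In SAP 7.4, replace the word asymptotic with exact (Clopper-Pearson) for all categorical endpoints. Wilson score intervals are a defensible alternative if the team prefers narrower intervals and accepts coverage that can fall to about 82% at some proportions; in that case the SAP should name Wilson. For cohorts of two or three subjects, showing counts alone would also be reasonable.

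The cost is one word in the SAP and one option in the program, with no new data. The intervals become wider (0/2 gives 0% to 84.2%), which is what two subjects can support. Clopper-Pearson is conservative, with coverage of at least 97.5% for n=2 to 5.

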7.5 Data Monitoring Committee (DMC)

Safety will be evaluated by the DMC prior to each dose escalation, prior to the first maintenance dose of each cohort, and prior to the enrollment of pediatric subjects by the DMC and Sponsor Medical Monitor. The DMC and Sponsor Medical Monitor will review data on an as needed basis as determined

by the Sponsor and in accordance with the protocol and DMC Charter. As such, a select number of Safety listings are produced for DMC meetings and Sponsor Medical Monitor reviews. The study's reviewing biostatistician will assist the committee members during the open sessions of the meetings in accordance with the DMC Charter.

7.6 Interim Analyses

An interim analysis of all outputs was conducted after the eighth subject in the study had at least 3 months of data in accordance with SAP version 1.0. The interim analysis included all available study data (all monitored and cleaned) at the time of the data snapshot, .

An additional interim analysis (interim analysis 2) of all outputs was performed using all available data (all monitored and cleaned) from all 11 subjects at the time of the data snapshot (ie, after mid-August 2018). SAP Version 1.0 was in effect at the time of this interim analysis.

A third interim analysis, consisting of all outputs produced for interim analysis #2, will be performed once the last subject has completed Visit 15 (end of study visit) and there is a soft lock. This third interim analysis (planned for August 2019) will consist of all outputs for interim analysis 2 and will include all available study data (all monitored and cleaned) at the time of the data snapshot.

No alpha or family-wise error rate adjustments are made for interim analyses at the data for this early phase 1b/2 trial as all analyses are exploratory.

7.7 Adjustments for Multiplicity

No adjustments for multiplicity will be made in this phase 1b/2 study.

8. Disposition of Subjects

Subject disposition will be summarized for the All Enrolled Subjects population. The number and percentage of subjects enrolled will be presented along with the number of subjects who screen fail. The number and percentage of subjects who receive QR-110 will be tabulated by the number of dosed subjects in each QR-110 cohort and dose group.

The number of subjects in each of the analysis populations (Safety and Efficacy) will be displayed by dose group and cohort and percentages will be calculated using all treated subjects as the denominator.

Any change from planned study dosing and maintenance dosing will be displayed on treatment listings by dose group. The subjects who prematurely discontinued from study drug will be summarized by dose group for all treated subjects. An AE listing of subjects who discontinue from study drug will also be presented. Treatment compliance will be displayed in listings and summarized on tables.

The number and percentage of subjects prematurely discontinued from the study and the reasons for study discontinuation will be summarized among treated subjects by dose group and cohort for all

subjects. The reasons for study discontinuation that will be summarized include: completed study, withdrawn prior to study drug, administrative reasons, sponsor termination of study, adverse event(s), protocol deviation(s), and other. A subject listing will be provided that includes the date of and reason for study discontinuation.

The number and percentage of subjects with major protocol deviations will be summarized among treated subjects by dose group. Major protocol deviations will be further summarized by category (e.g., visit conducted out of window) for all categories with one or more major protocol deviation. The protocol deviation categories include: informed consent, inclusion/exclusion, enrollment, subject was NOT treated with assigned treatment, assessment / procedure NOT conducted per protocol requirements, missed visit, visit conducted out of window, assessment not done, site failure to report AE/SAE, subject non-compliance and other. Protocol deviations related to inclusion/exclusion violations will have the specific criterion number indicated within the subject data listing. A subject listing will be provided that includes the date of the deviation, the deviation description and the classification of whether the deviation was judged to be major or minor.

In addition, subject listings will be provided that include informed consent date and inclusion and exclusion criteria violations.

9. Demographics

The demographic variables collected in this study include age, sex, childbearing potential, acceptable method of birth control, race and ethnicity. Subjects who record more than one race will be grouped into a single category denoted as multi-racial. Demographic variables will be summarized for the Safety Population, separately by dose group and cohort (Adult, Pediatric, and Combined).

Collection of date of birth depends on local regulations at study sites. In cases where only the year of birth is allowed to be collected, the month and day will be recorded in the eCRF as July 1 with the appropriate year.

Age (years) will be summarized, overall and by treatment, using continuous descriptive statistics. Age will also be categorized as follows: 6 years to <18 years, 18 years to <65 years and ≥65 years. Age will be reported in years and calculated using the following formula:

$$\text{Age} = (\text{informed consent date} - \text{date of birth}) / 365.25 \text{ truncated as an integer}$$

The number and percentage of subjects will be presented, overall and by treatment, for age category, gender, race and ethnicity.

A subject listing that includes all demographic variables will be provided for each dose group.

